11.3 Analytic Plan for Primary Objectives

SAEs defined by CTCAE v4.0 criteria within 90 days of ENCORE that are possibly/probably/definitely related to study treatment will be recorded. ENCORE therapy will be deemed safe if the rate of SAEs is $\leq 20\%$. An additional early stopping rule dictates that if 5 or more out of the first 10 patients develop ENCORE related SAEs, the trial will be halted.

The number of ICD therapies delivered in the 6 month periods preceding and following ENCORE therapy will be recorded for each patient by interrogation of the ICD. ENCORE therapy will be deemed efficacious if there is a reduction in ICD therapies before and after treatment. The proportion of patients with efficacious ENCORE therapy will be calculated, with the intent of demonstrating at least 40% efficacy.

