2.0 OBJECTIVES

2.1 Primary Objectives

1. Phase I - Demonstrate acute (≤ 90 days) safety of noninvasive stereotactic cardiac ablation radiotherapy (ENCORE). The **primary safety endpoint** is defined by a $\leq 20\%$ rate of serious adverse events (SAEs) using CTCAE v4.0 criteria that are possibly/probably/definitely related to study treatment, based on previously published data for expected invasive catheter-based VT-ablation procedures.
2. Phase II - Demonstrate preliminary efficacy of ENCORE. The **primary efficacy endpoint** is defined by the number of subjects with a reduction in ICD therapies (ATP and ICD shocks) comparing the period six months before ENCORE treatment to the six months after ENCORE treatment as adjudicated by continuous ICD monitoring. There will be a six-week “blanking period” after therapy to allow for ablation effect. For patients with PVC-induced cardiomyopathy, the primary efficacy will be any reduction in PVC burden based on ambulatory heart monitors.

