9.0 MEASUREMENT OF EFFECT

1. Acute (≤ 90 days) safety of ENCORE will be defined as a $\leq 20\%$ rate of protocol-specific serious or serious adverse events (SAEs) using CTCAE v4.0 criteria that are possibly/probably/definitely related to study treatment, based on previously published data for expected invasive catheter-based VT-ablation procedures. Early stopping rules have been created such that if 5 or more patients develop ENCORE related SAEs out of the first 10 patients, this would be deemed significantly greater than 20% ($\alpha < 0.05$), and the trial will be halted.
2. Preliminary efficacy of ENCORE will be defined by the number of subjects with a reduction in ICD therapies (six month period before ENCORE treatment compared to six month period after ENCORE treatment) as adjudicated by continuous ICD monitoring.

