11.0 STATISTICAL CONSIDERATIONS

11.1 Early Stopping Criteria

Through a one sample test for proportions, assuming a maximal clinically acceptable SAE rate of 20%, 5 or more SAEs out of the first 10 patients would be significantly greater than 20% ($\alpha < 0.05$). As such, the protocol will be halted if 5 or more of the first 10 patients develop a SAE.

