11.2 Sample Size Justification

A total of 19 patients will be enrolled, which provides an optimal balance between assuring a high likelihood of safety (Phase I) with a preliminary assessment of efficacy (Phase II).

For the phase I component, the baseline rate of SAEs for catheter ablation is assumed to be 10-15%. Given the population being studied and a reasonable expectation that patients may be at a higher than typical risk of toxicity from any salvage therapy, we assume that SAE rates up to 20% would be clinically acceptable. Having said that, given that this is a totally noninvasive technique, it may well be that rates of toxicity are lower than that expected with catheter ablation. After exploring patient ranges from 15-25 patients, it was determined that 19 patients would provide a 75.4% power to detect an SAE rate about 20% (range, 5%-20%, $\alpha = 0.0829$).

For the phase II component, while some single institution series report much higher success rates, the baseline efficacy rate of catheter ablation in prospective trials ranges from 50-65%. As this is a salvage therapy in a high risk population, we assume that efficacy rates as low as 40% would be clinically acceptable. Using the 19 patient sample determined above, it was determined that 19 patients would provide 81.5% power to determine that ENCORE is not worse than 40% effective for the treatment of VT (range, 40-65%, $\alpha = 0.0885$).

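### The alpha of 0.0829 and power of 75.4% in 11.2 fit a rule of at most 1 related SAE in 19; the written safety rule allows 3, and its error rates are not given

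*Combined protocol and SAP*

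**What the plan says.** Section 11.3 gives the primary safety decision: "ENCORE therapy will be deemed safe if the rate of SAEs is" at most 20%. Section 2.1 sets the same ceiling on the "rate of serious adverse events (SAEs) using CTCAE v4.0 criteria that are possibly/probably/definitely related to study treatment". Section 9.0 repeats it for the "rate of protocol-specific serious or serious adverse events (SAEs) using CTCAE v4.0 criteria" within 90 days. None of the three gives a critical count, a test or a confidence bound.

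Section 11.2 sets the size: "A total of 19 patients will be enrolled". On safety, "it was determined that 19 patients would provide a 75.4% power to detect an SAE rate about 20"%, with a range of 5% to 20% and alpha 0.0829. It adds that "we assume that SAE rates up to 20% would be clinically acceptable". It puts the catheter-ablation baseline at 10-15% and remarks that "it may well be that rates of toxicity are lower than that expected with catheter ablation", because the technique is noninvasive. Section 11.1 bases the stopping rule (5 or more of the first 10 patients) on "assuming a maximal clinically acceptable SAE rate of 20"%.

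**The concern.** An alpha and a power describe a particular decision rule. Section 11.2 attaches them to the safety objective without naming the rule, and section 11.3 names a rule without giving its error rates. A reader would naturally take 8.29% as the error rate of the safety conclusion that the trial will report. If the two sections imply different counts, that reading is wrong. Some results would then be called safe under 11.3 although the test that justified 19 patients had not shown a rate below 20%. This is the Phase I primary objective.

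The power sentence in 11.2 also appears to run the wrong way. It speaks of detecting a rate of about 20%, whereas a safety claim needs power to show that the rate is below 20%.

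**Working it through.** **Inputs.** n = 19, rates 5% and 20%, alpha 0.0829 and power 75.4% (11.2); observed rate at most 20% (2.1, 9.0, 11.3). X is the number of patients with at least one related SAE within 90 days, binomial with n = 19.

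**Step 1: reproduce 11.2.** Take the rule X ≤ 1, with P(X ≤ 1 | p) = (1−p)^19 + 19p(1−p)^18.

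- p = 0.20: 0.0144 + 0.0685 = 0.0829, the stated alpha.
- p = 0.05: 0.3774 + 0.3774 = 0.7547, the stated 75.4% apart from truncation.

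Neighbouring cut-offs do not fit: X ≤ 0 gives 0.0144 and 0.377; X ≤ 2 gives 0.2369 and 0.933. For n from 10 to 30, a lower-tail test against 20% gives 0.0829 only at n = 19 with X ≤ 1. The efficacy figures in 11.2 come from the same construction: X ≥ 11 of 19 gives 0.0885 at 40% and 0.8145 at 65%.

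**Step 2: turn the written rule into a count.** 3/19 = 15.8% passes and 4/19 = 21.1% fails, so the rule is X ≤ 3.

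**Step 3: compare the two rules.** The last column is P(X ≤ 3) − P(X ≤ 1), the chance of 2 or 3 events.

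| True related-SAE rate | Written rule, X ≤ 3 | Test behind 11.2, X ≤ 1 | Rules disagree |
|---|---|---|---|
| 5% | 98.7% | 75.5% | 23% |
| 10% | 88.5% | 42.0% | 46% |
| 15% | 68.4% | 19.8% | 49% |
| 20% | 45.5% | 8.3% | 37% |
| 25% | 26.3% | 3.1% | 23% |
| 30% | 13.3% | 1.0% | 12% |

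**Step 4: read the power sentence literally.** With a null of 5% and a rate of 20% to be detected, the nearest exact test is X ≥ 3 of 19. Its alpha is 0.0665 and its power 76.3%, so neither figure matches. The next cut-off, X ≥ 2, gives 0.245 and 91.7%. The 75.4% is therefore the power to show a rate below 20% when the truth is 5%. At a true 10% that power is 42%, and at 15% it is 20%. The plan states neither.

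**Step 5: stopping rule.** Five related SAEs in the first 10 patients already exceed 3, so a trial halted on related SAEs would fail the written rule anyway. The table does not change.

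**Step 6: precision at the limit.** The exact one-sided 95% upper limit is 22.6% at 1/19, 29.6% at 2/19 and 35.9% at 3/19.

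**The case against.** The strongest reply is that 11.2 only sizes the study and contains no decision rule. The limit of 1 in 19 is inferred, the three sections that do state a criterion agree with one another, and every figure in 11.2 is correct for its own test. With 2 or 3 events that test merely fails to show a rate below 20%; it does not call the treatment unsafe. All of that is true. But 11.2 attaches its alpha and power to this objective and threshold, and they are not the properties of the rule that will be applied.

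A second reply is that 20% in 11.3 could be the rate to be ruled out, with 11.2 supplying the test. Section 2.1 does speak of demonstrating safety. No section says this, however, and the observed-rate reading is the plainer one. If the test was intended, the cut-off still has to be written down.

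A third reply is that the plan accepts rates up to 20%, so 45.5% at exactly 20% is not a false declaration of safety on the plan's own terms. That stands. The wrong declarations are those above 20%, such as 26.3% at 25% and 13.3% at 30%.

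The denominator also deserves a caveat. Section 4.5 counts patients who complete the full dose as evaluable. With 15 to 18 evaluable patients the limit stays at 3, but the chance of declaring safety at a true 20% rises to between 65% (n = 15) and 50% (n = 18).

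Finally, this is a small early-phase study with a stopping rule and committee review, so one could call the correction desirable rather than essential. Because the point affects how the primary safety result is read, I would still require it.

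**Conclusion.** The concern holds. The alpha and power in 11.2 belong to a limit of 1 related SAE in 19, while the written criterion allows 3. At the 20% boundary the chance of declaring safety is 45.5%, against the 8.3% that 11.2 implies; at 5% it is 98.7% against 75.5%. The two rules part company at 2 or 3 events. Across the plan's own 10-15% baseline for catheter ablation, that outcome has a probability of 46-49%, so it is not a remote case. The power sentence is also reversed.

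This rests on three assumptions: the rate counts patients with at least one related SAE, all 19 are evaluable, and the observed proportion is compared directly with 20%. The limit of 1 is inferred, but no other cut-off or sample size examined reproduces the stated alpha.

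**What to change.** Reconcile 11.2 with 2.1, 9.0 and 11.3 in one of two ways, at the sponsor's choice.

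**(a) Keep the observed-rate criterion.** Write it as a count: at most 3 of 19 evaluable patients with a related SAE within 90 days. Remove alpha 0.0829 and power 75.4% from 11.2 and give the rule's own chance of declaring safety: 98.7% at 5%, 88.5% at 10%, 68.4% at 15%, 45.5% at 20%, 26.3% at 25% and 13.3% at 30%. Call the conclusion descriptive and report the exact one-sided 95% upper limit (35.9% at 3/19). The cost is wording in four sections and a less favourable error statement.

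**(b) Adopt the test behind 11.2.** State in 2.1, 9.0 and 11.3 that a rate below 20% is concluded if at most 1 of 19 patients has a related SAE within 90 days (exact one-sided binomial, alpha 0.0829). Report the upper limit at the matching level, 1 − 0.0829 = 91.7%, which is 20.0% at 1/19; the 95% limit of 22.6% would appear to contradict the conclusion. This changes the primary safety criterion and is much stricter. A treatment with a true rate of 10% or 15%, which the plan accepts, would fail 58% or 80% of the time. It therefore needs an amendment made without regard to accrued SAE data; the documents do not give accrual status.

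Either way, correct the reversed sentence. Under (b) it could read: *Power to show a related-SAE rate below 20% is 75.5% at a true 5%, 42% at 10% and 20% at 15%.* Under (a) the probabilities listed there replace it. Also say what applies if fewer than 19 patients are evaluable. Neither option needs more patients.

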Because of its invasive nature, there are risks to a catheter ablation procedure. Risks of serious complications include death (3%), stroke/transient ischemic attack (1-2%), cardiac perforation (1-2%), third-degree heart block (1.6%), pericardial effusion/tamponade (1%), worsening heart failure and cardiogenic shock (1-2%), uncontrollable VT (1%), and sepsis (<1%). Anecdotally, several centers report higher rates of adverse events in patients with more advanced and global cardiomyopathies. Future improvements in VT ablation technologies will need to address these significant adverse event rates, particularly among the sickest patients, and for those who have already failed traditional catheter ablation. A noninvasive approach to cardiac ablation has the potential to significantly improve safety and provide a viable option for VT refractory to ablation and medication. An attractive alternative to thermal ablation with radiofrequency energy may be noninvasive stereotactic radiotherapy.

[figure not shown]

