5.2 Serious Adverse Events (SAEs)

Definition: An adverse event that is any undesirable experience associated with the use of a medical product in a patient that results in death, hospitalization (new or prolonged), disability or permanent damage, or is life-threatening.

Specific to this protocol, SAEs are defined as AEs with CTCAE v4.0 grade 3 or higher resulting in hospitalization or grade 4-5 AE. Treatment-related SAEs were SAEs that are possibly, probably, or definitely related to protocol treatment.

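### A treatment-related death counts the same as a hospitalised grade 3 event, so the only numeric halting rule is not met by 2, 3 or 4 related deaths in the first 10 patients, and 3 related deaths in 19 can pass the safety verdict

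*Combined protocol and SAP*

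**What the plan says.** Section 5.2 sets the unit that is counted: "SAEs are defined as AEs with CTCAE v4.0 grade 3 or higher resulting in hospitalization or grade 4-5 AE". Attribution is broad: "Treatment-related SAEs were SAEs that are possibly, probably, or definitely related to protocol treatment". A related death is therefore one SAE, with the same weight as a grade 3 event that led to admission.

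Two rules use that count.

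- Final verdict (sections 2.1, 9.0 and 11.3). The window is "SAEs defined by CTCAE v4.0 criteria within 90 days of ENCORE", and "ENCORE therapy will be deemed safe if the rate of SAEs is" no more than 20%.
- Halting rule (sections 9.0, 11.1 and 11.3). Section 11.1 says "the protocol will be halted if 5 or more of the first 10 patients develop a SAE". Section 11.3 limits this to related events: "if 5 or more out of the first 10 patients develop ENCORE related SAEs, the trial will be halted". The difference does not affect this point, which concerns related deaths.

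Section 11.2 sets 19 patients and takes 20% as the highest acceptable SAE rate, raised from an assumed 10-15% for catheter ablation because this is a salvage population. No section gives an acceptable death rate. Section 1.2 lists death at 3% among the risks of catheter ablation, as background only.

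Other provisions touch deaths without a number attached: semi-annual DSMC review and ongoing monitoring by the principal investigator and coordinator (10.0), IRB reporting of a reportable death within one working day (5.7), tabulation by type and grade (11.4), and six- and twelve-month survival as a secondary endpoint (2.2).

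**The concern.** A 20% limit on a mixed category can be reasonable when most of the events are reversible. The same limit then also acts as the limit on deaths, because nothing else in the plan sets one. The plan scaled 20% from an all-SAE rate, so it was never justified as a tolerable death rate.

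Two consequences follow. During accrual, the one rule that halts the trial without anyone's discretion responds to deaths only at 5 of 10. At the end, a formula that ignores grade could report the primary safety objective as met when every counted event was a death. Section 1.7 says that this therapy has not been rigorously studied in a prospective trial, so both the halt and the verdict will carry weight.

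**Working it through.** **Inputs.** n = 19 and the 5% and 20% SAE rates (11.2); limit of at most 20% (11.3); halt at 5 or more of 10 against 20%, alpha below 0.05 (11.1); background catheter-ablation death risk of 3% (1.2). The 4-6% death rates below are assumptions that show the range.

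**Formula.** With X binomial(n, p), P(X ≥ r) = Σ from k = r to n of C(n,k) p^k (1−p)^(n−k).

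**Step 1: reproduce the plan's figures.**
- Halting rule: P(X ≥ 5 | 10, 0.20) = 0.0328, below 0.05; P(X ≥ 4 | 10, 0.20) = 0.1209, above it. Section 11.1 names only a one-sample test for proportions; the exact test gives its boundary of 5.
- Section 11.2: P(X ≤ 1 | 19, 0.20) = 0.0829 and P(X ≤ 1 | 19, 0.05) = 0.7547. These match the stated alpha of 0.0829 and power of 75.4%, so those figures belong to a cut-off of 1 or fewer SAEs in 19.

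**Step 2: apply the written rules to related deaths.**
- Halting: 2, 3 and 4 of 10 are all below 5, so the rule is not met.
- Verdict: 3/19 = 15.8% passes; 4/19 = 21.1% fails. The largest passing count is 3, and it passes with all three being deaths if no other patient has a related SAE. The exact 95% interval for 3/19 is 3.4% to 39.6%.
- At a true SAE rate of 20%, 3 or fewer of 19 occurs with probability P(X ≤ 3 | 19, 0.20) = 0.455, against 0.0829 for 1 or fewer.

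**Step 3: how the rules respond if the related SAEs are all deaths.**

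| True related-death rate | Halt: P(X ≥ 5 of 10) | Verdict passes: P(X ≤ 3 of 19) |
|---|---|---|
| 10% | 0.2% | 88.5% |
| 20% | 3.3% | 45.5% |
| 30% | 15.0% | 13.3% |

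**Step 4: the count that section 11.1's test gives for a declared death rate.** This is the smallest r with P(X ≥ r) below 0.05.

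| Declared rate | P(≥2 of 10) | P(≥3 of 10) | Count of 10 | P(≥3 of 19) | P(≥4 of 19) | Count of 19 |
|---|---|---|---|---|---|---|
| 3% | 0.0345 | 0.0028 | 2 | 0.0183 | 0.0022 | 3 |
| 4% | 0.058 | 0.0062 | 3 | 0.0384 | 0.0061 | 3 |
| 5% | 0.086 | 0.0115 | 3 | 0.0665 | 0.0132 | 4 |
| 6% | 0.118 | 0.0188 | 3 | 0.1021 | 0.0243 | 4 |

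(P(≥2 of 19) is 0.110 at 3%, so 2 is never the end-of-trial count in this range.) In the first 10, the count is 2 or 3 throughout, against 5 now. At 19, a count of 4 adds nothing, because 4/19 already fails the 20% limit. A separate death limit changes the verdict only at a declared rate of about 4% or less.

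**Step 5: chance of an unneeded pause.** This is the same tail probability read at the true rate. For 2 of 10 it is 3.5% at 3%, 5.8% at 4% and 11.8% at 6%. For 3 of 10 it is 0.6% at 4% and 1.9% at 6%.

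**The case against.** The strongest reply is that pooling grades is an explicit choice, made consistently in sections 2.1, 5.2, 9.0 and 11.3, and is not an error. That is right: the documents do not contradict themselves on how a death is counted.

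Oversight by judgement also exists. The DSMC includes a radiation oncologist, a cardiologist and a statistician and receives a toxicity summary; the principal investigator and coordinator monitor continuously; reportable deaths go to the IRB within a day. A reader might infer that the trial would simply run on through four related deaths. The documents do not support that: they show only that the numeric rule would not be met. What remains is that scheduled DSMC review is semi-annual, starting six months after accrual begins, and none of these provisions attaches a pause to a number of deaths.

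A reader might also take 3% as the plan's benchmark and call 3/19 five times the tolerated rate. Section 1.2 gives 3% as background for another procedure, without a time window or an attribution rule. It adds that centers report more adverse events in advanced cardiomyopathy, and the plan never adopts 3% as a limit. It serves here only as an illustration.

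A death trigger will also sometimes fire by chance or through generous attribution. Section 1.7 gives one-year survival below 20% for such patients. Under a constant hazard (an assumption) that means at least 1 − 0.20^(90/365) = 33% all-cause mortality by day 90, although exclusion criterion 6 should lower it. If 8-10% of patients died and were scored possibly related, 2 of 10 would be reached 19-26% of the time. This stands, and it is a reason for the sponsor to choose the rate with attribution in mind.

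Finally, the 3-of-19 example depends on section 11.3. Under the cut-off implied by section 11.2, 2 or 3 deaths would fail. This also stands, but that cut-off is nowhere written as the decision rule.

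**Conclusion.** The point holds for both written rules, most firmly for the halting rule. Two, three or four related deaths in the first 10 do not meet it, whereas section 11.1's own test would give 2 or 3 of 10 for any declared death rate from 3% to 6%. For the final verdict, 3 related deaths in 19 pass if section 11.3 governs and no other patient has a related SAE; the gap there is narrower.

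These are two separate scenarios. A reader might infer that a trial with 4 related deaths in its first 10 patients could still be declared safe. It could not: the final rate would be at least 4/19 = 21.1%, above the limit.

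The calculations assume one binomial count per patient and section 11.1's test read as exact. The 4-6% rates are assumptions, and 3% is not a limit in this plan. Severity: should fix, not must fix. The pooling is a stated design choice, oversight by judgement exists, and the acceptable death rate is for the sponsor to set.

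**What to change.** - **Section 11.1 (and 9.0).** Declare an acceptable related-death rate with its justification. Add a pause for DSMC review when related deaths in the first 10 patients reach the count that the exact test gives for that rate. State the attribution rule and who adjudicates.
- **Section 11.3.** State how related deaths enter the safety verdict. If a separate limit is used, note that it changes the verdict only at a declared rate of about 4% or less.
- **Sections 11.2 and 11.3.** Reconcile the written limit (3 or fewer of 19) with the cut-off behind the stated alpha and power (1 or fewer of 19), and give the operating characteristics of whichever rule is kept.
- **Reporting.** Show all-cause deaths to day 90 beside the related SAE rate, so that a reader can see how far the verdict depends on attribution.

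The cost is a few sentences and no new data, since events are already graded, attributed and followed. The downside is the chance of an unneeded pause worked out above: small for 3 of 10, up to 11.8% for 2 of 10 at a true rate of 6%, and higher if many deaths are scored possibly related. Because the action is a review and not a termination, that price is modest.

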2.2 Secondary Objectives

1. Determine six-month and twelve-month survival (**overall mortality endpoint**) after treatment with ENCORE.
2. Determine **late toxicity endpoint** (>90 days to 12 months), as tracked prospectively after treatment using CTCAE v4.0 criteria.
3. Determine patient-reported health related **quality of life endpoint** (HRQOL) as measured by changes between pre-treatment and 6-week, 6-month, and 12-month post treatment scores on the standardized SF-36 questionnaire.

4. Evaluate **stricter efficacy endpoint** of ENCORE treatment, as defined by number of patients who have had 50% reduction in any VT therapies (ATP or ICD shocks) after ENCORE treatment (6 months before vs. 6 months after treatment, with a 6 week blanking period immediately after treatment). For patients with PVC-induced cardiomyopathy, the stricter efficacy will be >50% reduction in PVC burden based on ambulatory heart monitors.
5. Evaluate **strictest efficacy endpoint** of ENCORE treatment, as defined by number of patients who have had 95% reduction in any VT (ATP or ICD shocks) after ENCORE treatment (6 months before vs. 6 months after treatment, with a 6 week blanking period immediately after treatment). For patients with PVC-induced cardiomyopathy, the strictest efficacy will be abolition of PVC burden (<1%) based on ambulatory heart monitors.
6. Evaluate the **most clinically useful efficacy endpoint** of ENCORE treatment, namely, number of patients with reduction specifically in ICD shocks (6 months before vs. 6 months after treatment, with a 6 week blanking period immediately after treatment). For patients with PVC-induced cardiomyopathy, the most clinically useful efficacy will be improvement in cardiac function in the setting of any improvement in PVC burden.
7. Evaluate **longer-term durability endpoint** of ENCORE treatment, as defined by number of patients with reduction in VT therapies (ATP or ICD shock and ICD shock alone) during the early phase (treatment to 6 months, with 6 week blanking period) vs. the late phase (6 months to 1 year). For patients with PVC-induced cardiomyopathy, the longer-term durability efficacy will be persistence of any reduction in PVC burden based on ambulatory heart monitors during early phase vs. late phase.

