4.5 Evaluability Guidelines

Patients who complete the full intended dose of single fraction SBRT are evaluable for both the primary and secondary objectives.

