4.9 Duration of Follow up

Patients will be followed per protocol for 12 months following the completion of SBRT or until death, whichever occurs first. Follow-up is per the treatment calendar (see Section 8.0) and consists of routine clinical visits, 12-lead EKG and implanted device interrogations to evaluate toxicity and treatment response, and evaluation of QOL. Patients will be followed by office visits, phone calls, and review of medical record. Any additional follow-up and imaging will be obtained off-study as per routine clinical policies of the treating physician. After 12 months, patients will be followed at the discretion of the treating physicians. Patients will be tracked for clinical outcomes up to 5 years after completion of radiation via review of the medical record.

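### The primary efficacy analysis leaves the blanking period out of the analysis sections, compares unscaled counts, gives no score for truncated follow-up, and does not state the success count behind its own alpha and power

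*Combined protocol and SAP*

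**What the plan says.** **Window.** Section 2.1 defines the primary efficacy endpoint by "comparing the period six months before ENCORE treatment to the six months after ENCORE treatment", and adds six weeks of blanking "after therapy to allow for ablation effect". Secondary objectives 4 to 6 in section 2.2 repeat the six-month comparison with the six weeks falling directly after treatment. Objective 7 describes the counts "during the early phase (treatment to 6 months, with 6 week blanking period) vs. the late phase (6 months to 1 year". Sections 9.0 and 11.3 define the same primary endpoint without blanking: 9.0 has "six month period before ENCORE treatment compared to six month period after ENCORE treatment", and 11.3 has "The number of ICD therapies delivered in the 6 month periods preceding and following ENCORE therapy will be recorded for each patient".

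**Success for a patient.** Any reduction in the number of ICD therapies. No section scales the count by time observed. Patients with PVC-induced cardiomyopathy are judged on PVC burden (2.1), so the window points concern ICD patients only.

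**Deaths.** Section 4.5: "Patients who complete the full intended dose of single fraction SBRT are evaluable for both the primary and secondary objectives". Section 4.9: "Patients will be followed per protocol for 12 months following the completion of SBRT or until death, whichever occurs first". No section says how a patient who dies before month 6 is scored.

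**Success for the trial.** Section 11.3 will calculate the proportion of responders "with the intent of demonstrating at least 40% efficacy". Section 11.2 gives n = 19, a range of 40-65%, alpha 0.0885 and power 81.5%. No section gives a number of responders.

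**The concern.** Each gap can change the primary result from the same device data.

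- If blanking removes six weeks from the post-treatment side only, the raw comparison favours treatment.
- If a patient dies early, the post-treatment count stops growing, so a bad outcome can be recorded as a response.
- If the 40% phrase is taken as an observed proportion, a result of 8, 9 or 10 of 19 is a success under section 11.3 but falls short of the count that gives section 11.2 its error rates.

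This is the primary endpoint of the phase II part, and it carries a stated alpha and power. The definition should therefore be fixed before the data are read.

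**Working it through.** **1. The plan's own figures.** Inputs from 11.2: n = 19, p0 = 0.40, p1 = 0.65. Exact one-sided binomial, P(X ≥ r):

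| r | observed share | at 0.40 (alpha) | at 0.65 (power) |
|---|---|---|---|
| 8 | 42.1% | 0.512 | 0.989 |
| 10 | 52.6% | 0.186 | 0.913 |
| 11 | 57.9% | 0.0885 | 0.8145 |
| 12 | 63.2% | 0.035 | 0.666 |

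Only r = 11 reproduces both stated figures. The smallest count with an observed share of at least 40% is 8, because 7/19 = 36.8%.

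**2. Window.** Six months = 182.625 days. Less 42 days of blanking this is 140.6 days, and 140.6/182.625 = 0.770. A stable rate therefore lowers the expected post-treatment count by 23%.

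**3. Share of patients with a reduction if treatment does nothing.** The documents give no therapy rate. Assumed: mean L = 5, 10, 20 or 50 therapies per six months, a stable VT rate, and at least 3 before treatment. That last condition simplifies inclusion criterion 4a, which also counts sustained VT and is dated to enrolment.

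Poisson: P(post < pre | pre ≥ 3), with pre ~ Poisson(L) and post ~ Poisson(0.770 L) or Poisson(L).

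| L | 5 | 10 | 20 | 50 |
|---|---|---|---|---|
| Blanked, raw counts | 0.658 | 0.667 | 0.755 | 0.879 |
| Equal windows | 0.494 | 0.456 | 0.468 | 0.480 |
| Blanked, as rates | 0.574 | 0.505 | 0.503 | 0.502 |

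Overdispersed: gamma patient rate with shape 1, gamma window effect with shape 2 or 1, 1,000,000 simulated patients per cell, 8 cells.

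- With the ≥3 condition: raw 0.61-0.74, equal windows 0.52-0.68, rates 0.53-0.71.
- Without it: raw 0.44-0.57.
- With the condition, the window itself adds about 0.07 to 0.10. The cell with mean 5 and shape 1 gives 0.743 − 0.677 = 0.066. The cell with mean 50 and shape 2 gives 0.612 − 0.517 = 0.095.

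If the VT rate rises 1.5-fold, the raw share falls to 21-40% (Poisson) or 46-64% (overdispersed, ≥3 condition).

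**4. Early death, treatment inert, literal count.** For a death at day 90 the expected post-treatment count is L × (90 − 42)/182.625 = 0.263 L with blanking and L × 90/182.625 = 0.493 L without. With the ≥3 condition, the chance of scoring as a reduction is:

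- Poisson: 96.5-100% blanked, 85-100% unblanked.
- Overdispersed: 84-94% blanked, 72-84% unblanked.

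Effect on the trial if two patients (number assumed) become automatic successes and the other 17 respond at 40%: success at 11/19 then needs 9 of 17, and P(X ≥ 9) = 0.199 against 0.088 with no such patients.

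**The case against.** The strongest reply is that the endpoint is defined once, in section 2.1, and that 9.0 and 11.3 abbreviate it. Much of this stands. Objectives 4 to 7 all place the blanking inside the six months, and 9.0 and 11.3 are silent on it without denying it. A reader might infer a further window of six full months starting at week 6. No section states one, and it would overlap the late phase that objective 7 starts at month 6. What remains is a mismatch to reconcile.

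Second, a reader might infer that an inert treatment would usually reach 11/19. That holds under Poisson counts with blanking and stable VT, where P(≥11/19) is 0.83 or higher. It does not hold generally. Under overdispersion much of the inert share comes from selecting patients with at least 3 prior therapies. Without that condition the share can be below one half, and a rising VT rate lowers it further.

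Third, 11/19 can be recovered from 11.2, and the verb used in 11.3 may mean a test against 40%. Both are fair. The sample size calculation is correct, and the fault is only that the decision count is left to inference.

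Fourth, a reader might project the one-year survival below 20% in section 1.7 onto these 19 patients. The documents do not support that. The figure is background for a wider population, and exclusion 6 removes patients unlikely to live 12 months, though only apart from their VT. Survival at six months is also a secondary objective, so deaths would be visible. They would still have no score in the primary endpoint.

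**Conclusion.** The point holds and should be fixed; it does not invalidate the study.

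- Three parts need no assumption about therapy rates: the blanking mismatch between 2.1 and 9.0/11.3, the missing score for truncated follow-up, and the gap between 8/19 (type I error 0.512) and 11/19 (0.0885).
- The 23% fall in expected count needs only the best-supported window and a stable VT rate.
- The size of the resulting bias depends on the model. It is large under Poisson counts (66-88% against 46-49% with equal windows) and modest under overdispersion (about 0.07 to 0.10).
- The tendency of early death to score as a reduction appears with or without blanking, but the number of such deaths is unknown.

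The harm is limited by the aim of the study, which is preliminary efficacy in 19 patients, and by the planned 95%-reduction endpoint. An inert treatment would meet that endpoint in 0-2% of patients (Poisson) or 3-22% (overdispersed), given at least 3 prior therapies.

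**What to change.** 1. In 11.3, state success as at least 11 of 19 responders (alpha 0.0885, power 81.5%).
2. In 2.1, 9.0 and 11.3, use one definition for ICD patients: therapies per month in the six months before treatment against therapies per month of observed device follow-up from week 6 to month 6. Use the same basis for secondary objectives 4 to 7. Keep the PVC-burden definition for PVC patients.
3. Count death before month 6 as non-response in the primary analysis, with the observed-time rate as a sensitivity analysis. A death before week 6 has no post-blanking time and stays a non-response there too. Prespecify how other truncated follow-up is scored, for example after heart transplant, which section 6.0 anticipates.
4. Add a caveat. Rate conversion removes only the window bias. With at least 3 prior therapies, an inert treatment would still show some reduction in 50-57% of patients (Poisson) or 53-71% (overdispersed). Show the planned 95%-reduction result alongside.

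**Cost.** Wording only. The study calendar already has device interrogation at 6 weeks, 3 months and 6 months, so counts can be split at week 6. The downside is a lower observed response rate and lower power if early deaths occur. With two deaths as non-responses and 65% response in the other 17, P(X ≥ 11 of 17) = 61.9%, against 81.5% with none.
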